6.4. Multicenter Studies

No planned analysis related to site will be conducted. This will be only performed upon request after datalock.

6.5. Multiple Comparisons/Multiplicity

This is an exploratory Phase 2 study; thus, multiplicity adjustment will not be performed.

6.6. Patient Population

Five patient populations are defined for the analyses in this study with detailed information listed in [Table GBGJ.2](#). Unless otherwise specified, listings will include all randomized patients. Efficacy and safety analyses will be conducted in the intent-to-treat (ITT) population. The primary efficacy measure (change from baseline in HbA1c) will also be evaluated in the per protocol (PP) population and Completer set (CS) population.

In all efficacy and hypoglycemia analyses, all data after rescue therapy will be censored unless otherwise stated.

Analyses of safety parameters, except for hypoglycemia events, will be conducted in the ITT population including the post-rescue therapy data.

Table GBGJ.2. Populations for Analyses

Population	Description
Entered	All participants who sign informed consent
Intent-to-treat	All participants who are randomized and take at least 1 dose of study medication for an assigned treatment arm
All randomized population	All patients who are randomized
Per protocol	
All ITT patients who meet all of the following criteria:
 
 • Have no important protocol deviation that could impact the assessment of the primary endpoint; the list of specific criteria is provided in Section 6.15 • At least 75% compliant with study drug administration • Complete the treatment period (18 weeks) • Have a value of the primary efficacy measure at 18 weeks 
Note: the final criteria will be documented in electronic Trial Master File (eTMF).

Completer set	All ITT patients who complete 18 weeks of study drug treatment without rescue therapy

Abbreviation: HbA1c = hemoglobin A1c; ITT = intent to treat.

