#### 7.4.1.3. Management of Patients with Severe, Persistent Hyperglycemia during the Treatment Period

An additional therapeutic intervention should be considered in patients who develop severe, persistent hyperglycemia after randomization based on the following criteria:

- a) average FPG >240 mg/dL (>13.3 mmol/L) over any 2-week period or longer during the first 6 weeks postrandomization; or
- b) average FPG >200 mg/dL (>11.1 mmol/L) over any 2-week period or longer after the first 6 weeks postrandomization.

Investigators should first confirm that the patient is fully compliant with the assigned therapeutic regimen and that he/she does not have an acute condition causing severe hyperglycemia. The investigator will decide in consultation with the patient on an appropriate glucose-lowering intervention (rescue intervention) after considering relevant clinical criteria. Other GLP-1 RAs or DPP-4 inhibitors must not be included in the rescue intervention (see [Table GBGJ.3](#) for allowed medications). Patients who receive a new intervention for hyperglycemia management should also continue administering study drug for the remaining period in the trial.

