Patients who stop the study drug permanently will receive another glucose-lowering intervention (rescue) and will continue participating in the trial according to the protocol to collect all planned efficacy and safety measurements.

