6.11.2. Additional Analyses of the Primary Outcome

6.11.2.1. MMRM in different populations

Different populations including ITT regardless of rescue therapy or adherence to study drug, PP, CS population will be evaluated separately using the same model as described in Section 6.1. The goal for these analyses is to assess the robustness of the primary outcome.

The output will be generated as that listed in Section 6.11.1.

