6.13. Safety Analyses

The safety analyses will include adverse events (AEs), serious adverse events (SAEs), AEs of special interest (AESIs), and treatment emergent adverse events (TEAEs), safety laboratory

analytes, vital signs, ECG. Adverse events of special interest include hypoglycemic and hyperglycemic episodes, pancreatitis, thyroid C-cell hyperplasia and C-cell neoplasms, allergic/hypersensitivity reactions, supraventricular arrhythmias and cardiac conduction disorders.

An AE will be coded using the Medical Dictionary for Regulatory Activities (MedDRA). TEAEs are defined as postbaseline events that are new events or preexisting conditions that worsened in severity after randomization using MedDRA low level term (LLT). The maximum severity level for baseline and post baseline for each same LLT term will be used as a criterion to determine TEAEs. If an AE occurs on the same date as the first dosing date with missing event occurring time, that event will be counted as post baseline event.

Unless otherwise specified, the ITT population will be used for analyses of safety measures, and all randomized population for data listing.

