Table GBGJ.3. Heart Rate, PR-Interval, and QTcF Abnormal Data

Parameter (Unit)	Visit	Threshold definition
HR (bpm)	Baseline (Visit 1)	>100, ≥ 130
	Post baseline	>100 and CFB >15
PR (msec)	Baseline (Visit 1)	≥ 220
	Post baseline	≥ 220
		≥ 220 and (%CFB >0 and $\leq 25\%$)
		≥ 220 and (%CFB >25%)
QTcF	Baseline (Visit 1)	> 450 (Male) or > 470 (Female)
		> 480
		> 500
	Post baseline	> 450 (Male) or > 470 (Female)
		> 480
		> 500
		>30 CFB
		>60 CFB

Abbreviations: QTcF = Fridericia's corrected QT interval.

Note: CFB means change from baseline; and %CFB is the percentage change from baseline.

The qualitative summary related to the treatment-emergent cardiac conduction and rhythm abnormalities will be reported by treatment. The abnormal ECG outcomes will be listed by treatment and patient.

A non-ITP Bayesian model will be fitted detailed in Section 6.11.2.3 with the priors: $\alpha, \beta[i, t] \sim N(0, 100)$ using 10000 MCMC samples with thin=10 and burn-in=10000. The probability of the posterior distribution of the parameter of interest on heart rate increase from baseline of each investigational dulaglutide dose compared to Dula 1.5 mg at Week 18.

$$pr(\Delta_i - \Delta_{dula1.5mg} < \text{threshold})$$

i stands for dulaglutide 3.0 mg/algorithm 1, dulaglutide 3.0 mg/algorithm 2, dulaglutide 4.5 mg/algorithm 1, and dulaglutide 4.5 mg/algorithm 2.

The threshold for this analysis will be 3bpm, 5 bpm, 7 bpm, 10 bpm.

The probability for Week 26 will be assumed to be the same as Week 18 from this model. The algorithm comparison at Week 6 will be evaluated.

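### Heart rate, pulse, BP, ECG intervals and pancreatic enzymes have no on-treatment analysis, so values taken after permanent stop of study drug shrink the Week 18 dose effects

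*SAP*

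**What the plan says.** SAP 6.6 sets two data rules. For efficacy: "In all efficacy and hypoglycemia analyses, all data after rescue therapy will be censored unless otherwise stated". For safety: "Analyses of safety parameters, except for hypoglycemia events, will be conducted in the ITT population including the post-rescue therapy data". SAP 6.13 adds no time limit: "Unless otherwise specified, the ITT population will be used for analyses of safety measures, and all randomized population for data listing".

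Protocol 8.1.1 determines who contributes values off drug: "Patients who stop the study drug permanently will receive another glucose-lowering intervention (rescue) and will continue participating in the trial according to the protocol". Rescue for hyperglycemia is different, because study drug goes on (protocol 7.4.1.3): "Patients who receive a new intervention for hyperglycemia management should also continue administering study drug for the remaining period in the trial".

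SAP 6.13.4.3 (pancreatic enzymes), 6.13.7.2 (ECG) and 6.13.7.3 (vital signs) specify MMRMs by visit. The last two sections add a Bayesian model, which reports "The probability of the posterior distribution of the parameter of interest on heart rate increase from baseline of each investigational dulaglutide dose" relative to 1.5 mg, as the probability that the difference lies below 3, 5, 7 or 10 bpm. SAP 6.16.2.2 uses the same thresholds against placebo at the interim. None of these sections limits values to time on drug.

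**The concern.** A patient who stopped study drug weeks before Week 18 cannot show the heart-rate or enzyme effect of the assigned dose, yet is analysed as if still on it. The mean effect moves toward zero in proportion to the off-drug share. Because the Bayesian output is the probability of lying below a threshold, a smaller estimate reads as more reassuring.

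The share may well differ by arm. Protocol 7.2.1 does not allow doses to be lowered and takes patients who fail rechallenge off study drug. Protocol 3.2 reports that 5 of 33 patients (15%) at 3.0 mg or higher in earlier studies stopped for GI events. Protocol 9.2.2.2 stops drug in supported pancreatitis but keeps the patient in the study, so those Week 18 enzymes are off-drug values.

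Protocol 3.2 names pancreatic enzymes, GI tolerability and heart rate as reasons why an earlier 3.0 mg arm was dropped. This trial is to support dose selection for Phase 3, and the interim shows heart-rate probabilities beside an HbA1c criterion that rests on rescue-censored data in the primary analysis.

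**Working it through.** **The analyses side by side**

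| Measure | Censored at rescue | All data | On treatment |
|---|---|---|---|
| HbA1c | yes (primary) | yes (SAP 6.11.2.1, 6.11.2.3) | PP and completer sets |
| FSG, body weight | yes | yes (SAP 6.11.3.2) | none |
| HR, pulse, BP, ECG intervals, enzymes | no | yes (the only rule) | none |

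The safety measures lack any version that leaves out off-drug values.

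**The plan's own figure.** The plan gives no precision figure for heart rate. Its HbA1c power claim (at least 90%) reproduces and is not in dispute: SE = 1.2 × √(2/60) = 0.219; 1.0/0.219 = 4.56; Φ(4.56 − 1.96) = 0.995.

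**Inputs from the protocol (3.2, 10.1).** Rise of about 5 bpm at 3.0 mg, estimated at 26 weeks from few patients; 2 to 4 bpm at 0.75 or 1.5 mg; about 60 completers per arm and 30 per dose/algorithm cell.

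**Assumptions.** 5 bpm is used as the Week 18 effect versus placebo; 3 bpm at 1.5 mg; off-drug share *f* among patients with a Week 18 value of 10% to 15% at 3.0 mg and 5% at 1.5 mg; full washout, which gives an upper bound; SD of change 8 to 10 bpm; normal approximation with a flat prior.

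**Dilution.** Mean seen = on-drug effect × (1 − *f*).
- Versus placebo: 5 × 0.90 = 4.5; 5 × 0.85 = 4.25. The loss is 0.5 to 0.75 bpm.
- Versus 1.5 mg, true gap 5 − 3 = 2.0: 4.5 − 3 × 0.95 = 1.65; 4.25 − 2.85 = 1.4. The loss is 0.35 to 0.6 bpm.

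**Against the noise.** With 60 per arm, SE = SD × √(2/60) = 1.46 to 1.83 bpm. With a cell of 30 against 60, as in the final Bayesian model, SE = SD × √(1/30 + 1/60) = 1.79 to 2.24 bpm. The largest loss, 0.75 bpm, is about half of the smallest SE (0.75/1.46 = 0.51).

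**Effect on the reported probabilities.** Pr = Φ((threshold − mean seen)/SE); ranges cover SD 8 to 10.

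| Quantity | On drug only | *f* = 10% | *f* = 15% |
|---|---|---|---|
| Pr(< 5 bpm vs placebo), 60 v 60 | 0.50 | 0.61–0.63 | 0.66–0.70 |
| Pr(< 5 bpm vs placebo), interim, about 30 v 30 | 0.50 | 0.58–0.60 | 0.61–0.64 |
| Pr(< 3 bpm vs 1.5 mg), cell of 30 v 60 | 0.67–0.71 | 0.73–0.78 | 0.76–0.81 |

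**What is not affected.** The enzyme shift table on the maximum post-dose value cannot fall when later values are added. At Weeks 6, 8 and 10 fewer off-drug values can have accumulated.

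**The case against.** A reader might infer that risk is diluted while benefit is left wholly undiluted. The documents do not support that. Efficacy is cut at rescue, not at drug stop, so values between stopping and rescue, or during a temporary interruption, remain. All-data efficacy analyses are also planned: for HbA1c, "Different populations including ITT regardless of rescue therapy or adherence to study drug, PP, CS population will be evaluated separately", plus the Bayesian model, and an uncensored repeat for FSG and weight. Benefit and heart rate can already be compared on an all-data basis. What is missing is the on-treatment counterpart on the safety side.

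A reader might also take post-rescue to mean off drug. Patients rescued for hyperglycemia continue study drug, so much of the retained post-rescue data may be on drug. The point rests on protocol 8.1.1 together with SAP 6.6, not on the SAP sentence alone.

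The exposure-response work (protocol 10.3.5; SAP 6.16.2.2) relates dose or concentration to QT, BP and heart rate and need not treat an off-drug patient as dosed. This helps in part, but it names no pancreatic enzymes and its details are in a separate plan (SAP 6.12).

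No decision rule is tripped. The heart-rate thresholds carry no required probability, the committee weighs all the safety data, and SAP 6.7 tabulates drug discontinuation by arm and visit, so differential stopping will be visible.

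Finally, the 5 of 33 comes from earlier studies, whereas this trial titrates in order to reduce GI events. It is a stopping rate, not the share measured off drug at Week 18; patients who leave through the early-termination visit may have no Week 18 value. All of this limits the size and reach of the point. It does not supply the missing analysis.

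**Conclusion.** The point holds as a one-sided gap. Off-drug values enter the by-visit MMRMs and the heart-rate and pulse-rate probabilities under the assigned dose, the primary efficacy analysis mostly drops such values once rescue starts, and no on-treatment safety analysis is planned. The bias in Week 18 means is toward no dose effect, and it grows with the discontinuation rate of the arm.

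The size cannot be fixed from the documents. Under the stated assumptions the loss is 0.35 to 0.75 bpm, below one standard error, and it is smaller if washout is incomplete or fewer patients are off drug. The documents give no heart-rate figure for 4.5 mg, so a larger loss there would be conjecture. The shift is systematic and feeds a dose-selection readout, which makes it worth correcting at small cost. It does not invalidate the planned ITT safety analysis.

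**What to change.** In SAP 6.6, 6.13.4.3, 6.13.7.2, 6.13.7.3 and 6.16.2.2, add a supplementary on-treatment analysis of heart rate, PR interval, QTcF, pulse rate, BP, amylase and lipase:

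- For patients who permanently stop study drug early, exclude values later than a prespecified interval after the last injection, for example one dosing interval, with a longer washout as a sensitivity check.
- Keep all Visit 12 values of treatment completers.
- Base the flag on the last injection, not on rescue, so that patients rescued for hyperglycemia and still on drug are kept.
- In Table APP1.1, state that window end B (end of the maintenance phase) is not the last dose date, or define it. If it were read as the last dose, later values would leave the Week 18 window.
- Keep the ITT version alongside. In the interim and dose-selection tables, show efficacy and heart rate on matching rules: rescue-censored beside on-treatment, and all-data beside all-data.

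The cost is SAP wording, one data flag and a repeat of planned models. SAP 6.13.1 already uses actual dosing dates. The downside is fewer observations and a comparison no longer on all randomised patients, which is why the ITT result stays.

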6.7. Patient Disposition

The reasons for patient discontinuations from study medication and from the study will be summarized for all randomized subjects by each randomized treatment, by visit, and overall. An additional report will be provided to provide combined disposition report for early discontinuation of study drug and early discontinuation of study, by visit, cumulative and overall. The latter report is needed to account for patients who permanently discontinue study drug but continued in the trial, as allowed by the study protocol.

The p-value to test the overall treatment effect among all randomized treatments and the p-value will be presented using Fisher's exact test or Chi-square test detailed in Section 6.1.

Kaplan-Meier curves by treatment for time to study discontinuation due to any reason will be presented. The log-rank p-value will be presented.

In addition, all entered patients will be summarized including, but not limited to, the total number of patients screened (entered) and the number of patients excluded due to screen failure.

Patient disposition will be listed for all randomized population.

6.8. Patient Characteristics

Demographic and baseline clinical characteristics will be summarized by treatment for ITT population detailed in Section 6.1. For continuous measures, summary statistics will include sample size, mean, median, maximum, minimum, and SD along with the ANOVA p-value to test for difference among all randomized treatment groups. For categorical measures, summary statistics will include sample size, the number and percentage of patients for each category with Fisher's or Chi-square p-value. In the summary report, each algorithm arm will be included.

Similar summary reports will be generated separately for PP and CS population.

The patient characteristics will be listed for all randomized population.

6.9. Treatment Compliance

Treatment compliance in GBGJ is defined as taking at least 75% of the required injections for the prespecified time intervals: titration phase from the first dose to the sixth dose, and every 4 weeks thereafter: from the seventh dose to the 10th dose, from the 11th dose to the 14th dose, from the 15th dose to the 18th dose. Overall compliance is defined as being at least 75% compliant with investigational product across the treatment period. Compliance source data is from the site reported case report form (CRF) data.

Compliance will be summarized using ITT population by each randomized treatment and time interval, and overall. Listings will also be produced from all randomized population.

6.10. Concomitant Therapy

The prespecified concomitant medications of interest will be summarized (detailed in Section 6.1) by all randomized treatments groups for baseline and after randomization, for the ITT population. In addition, antihyperglycemia medications will be also summarized at screening and for the last 3 months prior to study enrollment by each randomized treatment group. The concomitant therapies will be mapped using the World Health Organization (WHO) DRUG dictionary in the clinical trial database and will be further classified using Anatomic-Therapeutic-Chemical (ATC) codes for reporting purposes.

The agents of interest for the summary report include the following groups of medication:

- antihyperglycemia agents
 - background metformin therapy
 - agents used for short term therapy for acute condition
 - rescue therapy (only applicable for after randomization)
 - agents used for other reasons
- weight loss medications
- systemic glucocorticoids
- antihypertensive agents
- lipid lowering agents
- anticoagulant agents
- anti-inflammatory agents
- cardiac therapy

Concomitant therapy will be listed for the all-randomized population.

6.11. Efficacy Analyses

6.11.1. Primary Outcome and Methodology

The primary analysis for the primary outcome, change from baseline in HbA1c at Week 18 (Visit 12), will employ MMRM described in Section 6.1 in ITT population by censoring all post rescue data.

The report from this analysis includes LS means and corresponding 95% CIs for each randomized treatment at each scheduled visit, and the difference in LS means, corresponding 95% CI along with p-value compared to placebo and to dulaglutide 1.5 mg at the same visit.

6.11.2. Additional Analyses of the Primary Outcome

6.11.2.1. MMRM in different populations

Different populations including ITT regardless of rescue therapy or adherence to study drug, PP, CS population will be evaluated separately using the same model as described in Section 6.1. The goal for these analyses is to assess the robustness of the primary outcome.

The output will be generated as that listed in Section 6.11.1.

6.11.2.2. Missing data imputation

If the conclusions differ among the four populations listed in Section 6.11.1 and Section 6.11.2.1, additional analyses may be further explored using selected pattern mixture models for missing data (Kenward and Rosenkranz 2011) in the ITT population regardless of rescue therapy or compliance to the study treatment. In this case, imputed 18-week HbA1c response for the missing data along with the non-missing 18-week data will be employed using an ANCOVA model by removing all visit related terms. The missing data will be imputed from the non-missing subjects who took rescue therapy or continued on the study but discontinued study medication. Depending on the missing data status, the non-missing data used for imputation may be altered from what is described in this section.

The tipping-point approach is like a progressive stress-test to assess how severe departures from missing at random (MAR) need to be in order to overturn conclusions from the primary analysis. In the dulaglutide arms, the imputed values will be replaced by the imputed value plus a shift parameter beginning from 0 with the increment of 0.05. Each value of the shift parameter will be tested sequentially until the value is reached at which the conclusion from the MMRM analysis is reversed. That value is the tipping point indicating that the conclusion under MAR is questionable if this shift parameter value is plausible. If implausible departures from MAR are required to change the results from statistically significant ($p \leq 0.05$) to not statistically significant ($p > 0.05$), the results will be said to be robust to the departure from MAR assumption and provide more confidence in the results obtained based on statistical methods with the MAR assumptions.

6.11.2.3. Bayesian Analyses For Exploratory Objectives

A Bayesian integrated 2-component prediction (ITP) model (Fu and Manner 2010) will be fitted for the primary endpoint separately in ITT population by censoring all post rescue therapy data,

and in ITT population including all available data regardless of rescue medication or adherence to the study drug. Non-informative priors will be used in this model. In addition, the informative priors from the posterior for placebo and posterior for dulaglutide 1.5 mg obtained from Study H9X-MC-GBCF (GBCF) and Study H9X-MC-GBDE (GBDE) will be evaluated in this model to check the robustness of the analysis.

$$Y_{ijt} = (\theta_i + S_{ij} + \alpha \times (B_{ij} - \bar{B}) + \varepsilon_{ijt}) \times \left(\frac{1 - e^{k_i \times t}}{1 - e^{k_i \times 18}} \right)$$

Prior information: $\theta_i, \alpha \sim N(0, 3)$; $S_{ij}, \varepsilon_{ijt} \sim \text{uniform}(0.01, 3)$; $k_i \sim \text{uniform}(-1, 1)$ where Y_{ijt} represents HbA1c change from baseline from dose i , subject j at time t . Parameter θ_i is the predicted drug effect of dose i at 18-week therapy. The parameter S_{ij} is a random between-subject SD, and ε_{ijt} is the within subject SD. The B_{ij} is baseline HbA1c for subject j at dose i and \bar{B} is the overall arithmetic mean baseline HbA1c from all subjects. k_i is the parameter to represent how fast to reach the effect for dose i at Week 18.

Probabilities based on posterior distributions of the parameter of interest: change from baseline to Week 18, and Week 26 will be generated from this model using 10000 MCMC samples with thin=10 and burn-in=10000:

$$\text{pr}(\Delta_i - \Delta_{\text{dula1.5mg}} < \text{threshold})$$

i stands for dulaglutide 3.0 mg or 4.5 mg.

The threshold of -.15, -.2, and -.3% will be used, separately.

If this model fails to converge, an alternative Bayesian model will be fitted:

$$y_{ijt} \sim MVN(\mu[i, t], \Omega)$$

$$u[i, t] = \alpha \times (B[i, t] - \bar{B}_0) + \beta[i, t] \times T[i, t]$$

Where $\beta[i, t]$ is the effect for dose i at time t . Ω is the variance-covariance matrix.

The priors for each parameters are: $\alpha \sim N(0, 3)$, $\beta[i, t] \sim N(0, 3)$, $\Omega \sim \text{wishart}(t, t\text{-demension Identity matrix})$.

The probability for Week 26 will be assumed to be the same as Week 18 from this model.

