## 2. Schedule of Activities

Visit	Screening and Lead-In		Treatment Period										Follow-Up	
	1	2	3	4	5	6	7	8	9	10	11	12	801	ET a
Week of Treatment	-2	-1	0	2	4	6	7	8	9	10	14	18	22	ET
Allowable Deviation (Days)b	±3	±3		-3	-3	-3	±3	±3	±3	+4	±7	±7	±3	
Informed consent	X													
Randomization c			X											
Clinical Assessments														
Medical History	X													
Physical	X													
Height	X													
Weight	X		X	X	X	X	X	X	X	X	X	X	X	X
Vital Signs (3 sitting BP and PR measurements)	X		X	X	X	X	X	X	X	X	X	X	X	X
Electrocardiogram d	X					X		X		X		X		X
Adverse events		X	X	X	X	X	X	X	X	X	X	X	X	X
Concomitant medications	X	X	X	X	X	X	X	X	X	X	X	X	X	X
Review/record hypoglycemic events			X	X	X	X	X	X	X	X	X	X	X	X
Remind patients about 6-point SMPG		X									X			
Record 6-point SMPG values e			X									X		X f
Patient summary												X	X	X
Patient Education and Management														
Dispense study diary, instruct in use		X	X			X				X	X	X		
Review study diary			X	X	X	X	X	X	X	X	X	X	X	X
Return study diary			X			X				X	X	X	X	X
Diabetes management education g		X												
PG meter, SMPG training g		X	X											
Review SMPG values			X	X	X	X	X	X	X	X	X	X	X	X
Injection training g		X	X											
Dispense PG meter/supplies		X	X	X	X	X	X	X	X	X	X	X		
Dispense study drugs and/or injection supplies			X	X	X	X				X	X			
Observe patient inject study drug h			X											

Visit	Screening and Lead-In		Treatment Period										Follow-Up		
	1	2	3	4	5	6	7	8	9	10	11	12	801	ET a	
Week of Treatment	-2	-1	0	2	4	6	7	8	9	10	14	18	22	ET	
Allowable Deviation (Days)b	±3	±3		-3	-3	-3	±3	±3	±3	+4	±7	±7	±3		
Patient Education and Management (concluded)															
Patient returns study drugs and/or injection supplies				X	X	X	X	X	X	X	X	X		X	
Assess study drug compliance i				X	X	X	X	X	X	X	X	X		X	
Laboratory tests															
Serum pregnancy test j	X														
Urine pregnancy test k			X												
Follicle-stimulating hormone test l	X														
Chemistry panel	X											X		X	
Lipid panel (fasting) m			X									X		X	
Urinalysis	X											X		X	
Albumin/creatinine ratio (urine) n	X											X		X	
eGFR (CKD-EPI) o	X											X		X	
Hematology	X											X		X	
Immunogenicity			X			X						X	X	X	

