5.2. Determination of Sample Size

Assuming a screen failure rate of 30%, approximately 429 patients will need to be screened to attain approximately 300 patients randomized to the 4 treatment arms in a 1:1:1:1 ratio for 4.5 mg, 3.0 mg, 1.5 mg dulaglutide, or placebo weekly (~75 patients per arm). For the investigational dulaglutide dose arms (4.5 mg and 3.0 mg), approximately 38 patients will be assigned to each titration algorithm (Algorithms 1 and 2). Assuming a 20% dropout, this will result in approximately 60 patients per arm and 30 patients per algorithm (in each of the investigational-dose dulaglutide arms) completing the study.

The aforementioned sample size provides $\geq 90\%$ power to demonstrate superiority for the dulaglutide doses (4.5 mg, 3.0 mg, and 1.5 mg) to placebo with respect to HbA1c change from baseline to 18 weeks. This assumes a true glycemic effect difference of -1% HbA1c for each dulaglutide dose versus placebo, and a standard deviation (SD) of 1.2% with a 2-sided alpha of 0.05.

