6.13.7.2. Electrocardiograms

Heart rate (HR), PR interval (PR), and QT corrected for heart rate using QTcF are collected in triplicates. Prior to any analysis, the arithmetic mean from the three measures for the same parameter at the same visit will be calculated and use for all subsequent analysis. MMRM model detailed in Section 6.1. for continuous variable analysis will be used to analyze each parameter in change from baseline. The treatment in the model will be placebo, dulaglutide 1.5 mg, dulaglutide 3.0 mg/algorithm 1, dulaglutide 3.0 mg/algorithm 2, dulaglutide 4.5 mg/algorithm 1, dulaglutide 4.5 mg/algorithm 2.

The reports for these analyses will include:

- LS means and corresponding 95% CIs for each randomized treatment at each scheduled visit, and the difference in LS means, corresponding 95% CI along with p-value compared to placebo and to dulaglutide 1.5 mg at the same visit.
- LS means and corresponding 95% CIs of each parameter's effect for algorithm 1, algorithm 2, and the difference between algorithm 2 and algorithm 1 (using algorithm 1 as reference) at Week 6 (Visit 6). These results will not be acquired directly from the MMRM model. Rather, they will be obtained from the same model by forming appropriate estimate statements with the same algorithm across dulaglutide 3.0 mg and dulaglutide 4.5 mg.
- LS means and corresponding 95% CIs of each parameter's effect for dulaglutide 3.0, dulaglutide 4.5, and the difference between each combined treatment across algorithms and Placebo, and the difference between each combined treatment to Dula 1.5 at the same Week (Visit): Week 8 (Visit 8), Week 10 (Visit 10) and Week 18 (Visit 12). These results will be obtained through the same model by forming appropriate estimate statements for the same dose across different algorithms.
- The difference in LS means and the corresponding 95% CIs along with the p-value between each maintenance visit (Week 8/Visit 8, Week 10/Visit 10, Week 18/Visit 12) and the end of titration (Week 6/Visit 6) within the same treatment including the combined dulaglutide 3.0 mg and 4.5 mg, and within the same algorithm will be presented. Any result related to combined treatment across algorithms and each algorithm at Visit 6 (Week 6) will be formed by constructing an appropriate estimate statement.

The threshold analysis will only include HR, PR by visit and by randomized treatment, dulaglutide 3.0, and dulaglutide 4.5 mg. The threshold is defined in [Table GBGJ.3](#).

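### SAP 6.11.2.3 places a Wishart(t, identity) prior on the covariance matrix itself; carried to heart rate and pulse rate in bpm, it shrinks the variance and makes the supplementary Bayesian probabilities overconfident

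*SAP*

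**What the plan says.** SAP 6.11.2.3 specifies the integrated two-component prediction (ITP) model for HbA1c and, if that fails to converge, an alternative: a multivariate normal with mean μ and matrix Ω. It states that Ω "is the variance-covariance matrix". The prior then listed for Ω is a Wishart with t degrees of freedom, its scale being the t-"demension Identity matrix". The text gives no inverse, no precision matrix and no other scale.

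For HbA1c and body weight (SAP 6.11.2.3 and 6.11.3.3) this alternative is only a fallback. For ECG heart rate it is the Bayesian model that is planned from the outset: "A non-ITP Bayesian model will be fitted detailed in Section 6.11.2.3 with the priors" N(0, 100) for α and β (SAP 6.13.7.2). SAP 6.13.7.3 does the same for pulse rate. Neither section gives a new prior for Ω, so the identity-scaled Wishart carries over.

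The output is the posterior probability that an investigational dose, by titration algorithm, exceeds dulaglutide 1.5 mg by less than a threshold at Week 18: "The threshold for this analysis will be 3bpm, 5 bpm, 7 bpm, 10 bpm". SAP 6.16.2.2 plans the same type of probability against placebo at the efficacy/safety interim, without naming a model.

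**The concern.** A Wishart prior is the usual conjugate choice for a precision matrix. Placed on a covariance matrix with identity scale, its density falls as exp(−tr Ω / 2). On the HbA1c scale, with variances near 1, this does little. For heart rate, with variances of perhaps 50 to 150 bpm², the penalty is large enough to compete with the data.

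A fitted variance that is too small gives a posterior for the dose difference that is too narrow. When the observed increase lies below the threshold, the chance that the true increase is below it is overstated; when it lies above, that chance is understated. Heart rate matters here: Protocol 3.2 names it among the effects that led to early discontinuation of the 3.0 mg arm in an earlier study.

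**Working it through.** **The plan's own figure.** No stated figure depends on this prior. The one design figure that can be reproduced is the HbA1c power of at least 90%: with 60 completers per arm, difference 1.0 and SD 1.2, power is 0.995, so the stated bound holds. It has no bearing on this point.

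**Inputs from the documents.**
- ECG: t = 4 post-baseline visits, from "Week 8/Visit 8, Week 10/Visit 10, Week 18/Visit 12) and the end of titration (Week 6/Visit 6" in SAP 6.13.7.2.
- Pulse rate: t = 9, counting Visits 4 to 12 in the row "Vital Signs (3 sitting BP and PR measurements" of the Protocol's Schedule of Activities and leaving out follow-up.
- Final analysis: "approximately 60 patients per arm and 30 patients per algorithm" (SAP 5.2), so n = 240 completers, and 30 against 60 for one dose and algorithm against 1.5 mg.
- Interim: about 120 patients, so 120/4 = 30 per arm.

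**Assumed, because the documents give neither:** SD of change in heart rate 7 to 12 bpm and equal between-visit correlation 0.3 to 0.7. The worked case uses SD 9 and correlation 0.6.

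**Effect of the literal prior.** With t × t matrices, the Wishart(t, I) density is proportional to |Ω|^(−1/2) exp(−tr Ω / 2). Multiplying by the normal likelihood and maximising gives, for each eigenvalue s of the data covariance, a fitted eigenvalue l that solves

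l² + (n + 1)l − ns = 0.

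Under equal correlation ρ there is one eigenvalue SD²[1 + (t − 1)ρ] and there are t − 1 eigenvalues SD²(1 − ρ). The fitted variance at a visit is [l₁ + (t − 1)l₂]/t.

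Worked case, ECG: s₁ = 81 × 2.8 = 226.8 and s₂ = 81 × 0.4 = 32.4.
- n = 240: l₁ = 142.1, l₂ = 28.8; variance (142.1 + 3 × 28.8)/4 = 57.1; SD 7.56; ratio 0.840.
- n = 120: l₁ = 115.2, l₂ = 26.4; variance (115.2 + 3 × 26.4)/4 = 48.6; SD 6.97; ratio 0.775.

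For pulse rate (t = 9) the ratios are 0.800 and 0.737.

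Ratio of fitted to true SD over the assumed ranges:

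| | n = 240 | n = 120 |
|---|---|---|
| ECG heart rate, t = 4 | 0.77 to 0.91 | 0.70 to 0.86 |
| Pulse rate, t = 9 | 0.72 to 0.90 | 0.65 to 0.84 |

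The mode is a fair summary. For SD 10, correlation 0.5 and t = 4 it gives 8.36 and 7.69, and a Metropolis run gave posterior mean SDs of 8.42 (n = 240) and 7.77 (n = 120). With an inverse-Wishart(t, I) prior on Ω instead, the SDs are 10.01 and 10.02, so the shrinkage disappears.

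**Effect on the probabilities (ECG, SD 9, correlation 0.6).** The SE of a difference is SD × √(1/n₁ + 1/n₂), and Pr(difference < 5) = Φ[(5 − observed)/SE].
- Final, 30 v 60, observed +3: SE 2.01 becomes 1.69; Φ(0.99) = 84% becomes Φ(1.18) = 88%.
- Final, 30 v 60, observed +6: Φ(−0.50) = 31% becomes Φ(−0.59) = 28%.
- Interim, 30 v 30, observed +3, if this model is used: SE 2.32 becomes 1.80; Φ(0.86) = 81% becomes Φ(1.11) = 87%.

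A nominal 95% interval then covers 2Φ(1.96 × ratio) − 1, which is about 90% at the final analysis (ratio 0.840) and 87% at the interim (0.775). With the nine-visit pulse-rate ratios the shifts for an observed +3 are slightly larger: 84% to 89% and 81% to 88%.

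**Other endpoints.** HbA1c with SD 1.2, t = 3, n = 240: fitted SD 1.19 against 1.20. Body weight, if its fallback is needed, with assumed SD 3 to 4 kg, t = 9 and correlation 0.7: ratio 0.93 to 0.90.

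**The case against.** The best reply is that the section is shorthand and the programmer will put the Wishart on the inverse of Ω, as common Bayesian software does. If the normal priors are also read as mean and variance, both are sensible and only the description of Ω is wrong. That reading is coherent, and under it the results are sound. It is not what the SAP says, however. Nor does reading everything as precision rescue the text: N(0, 100) would then have SD 0.1. With 75 per arm it would keep 0.01/(0.01 + 81/75) = 1% of an observed heart-rate effect (assumed SD 9) and 0.01/(0.01 + 16/75) = 4% of a weight effect (assumed SD 4). The text needs correcting whichever reading was meant.

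It is also true that these probabilities are supplementary. SAP 6.13.7.2 and 6.13.7.3 analyse heart rate and pulse rate by MMRM, with intervals and p-values, and SAP 6.16.2.2 reports MMRM results for selected ECG and vital-sign measures at the interim. An unaffected estimate will stand beside each probability.

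Four stronger readings are tempting, and the documents do not support them:
- That this is the main heart-rate analysis. It is not; the MMRM has a full set of comparisons.
- That an interim safety criterion is wrong. SAP 6.16.2.2 names no model for heart rate or pulse rate, compares with placebo rather than 1.5 mg, and sets no probability cut-off for them. The study will not be stopped on the interim efficacy results (SAP 6.16).
- That the SAP contradicts itself with "Non-informative priors will be used in this model". That sentence describes the ITP model and precedes the alternative one.
- That the error always reassures. It sharpens the probability in both directions, as the +6 bpm case shows.

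**Conclusion.** The point stands as an error in a stated analysis rule. Read literally, SAP 6.11.2.3 gives a covariance matrix a prior that shrinks it, and SAP 6.13.7.2 and 6.13.7.3 carry that prior to bpm-scale data. The size is moderate: a fitted SD about 9% to 28% too small at the final analysis and 14% to 35% too small with 120 patients, and probabilities about 3 to 6 points further from 50% in the central ECG cases. These figures rest on an assumed heart-rate SD and correlation, complete data, and literal implementation. The primary HbA1c analysis and all MMRM results are unaffected, and no decision in the documents is shown to change. It is worth correcting because the probabilities cannot be reproduced from the text without guessing, and the literal guess is miscalibrated.

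**What to change.** - In SAP 6.11.2.3, assign the Wishart prior to Ω⁻¹, or an inverse-Wishart prior to Ω.
- In SAP 6.13.7.2 and 6.13.7.3, give a scale matrix suited to bpm, and one suited to kg in 6.11.3.3 in case the body-weight fallback is used. Moving the prior to the inverse does most of the work; the scale makes the prior explicit for each endpoint.
- State that the second argument of N(0, 3) and N(0, 100) is a variance.
- In SAP 6.16.2.2, name the model behind the interim heart-rate and pulse-rate probabilities.
- Add a short prior-sensitivity check for the bpm endpoints.

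The cost is SAP wording and one extra model run per endpoint. No data collection, sample size or primary analysis changes.
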